4.6.3 Study Discontinuation

The Sponsor has the right to terminate this study at any time. Reasons for terminating the study may include, but are not limited to, the following:

- The incidence or severity of adverse events in this or other studies indicates a potential health hazard to patients
- Patient enrollment is unsatisfactory

The Sponsor will notify the investigator if the Sponsor decides to discontinue the study.

4.6.4 Site Discontinuation

The Sponsor has the right to close a site at any time. Reasons for closing a site may include, but are not limited to, the following:

- Excessively slow recruitment
- Poor protocol adherence
- Inaccurate or incomplete data recording
- Non-compliance with the International Council for Harmonisation (ICH) guideline for Good Clinical Practice
- No study activity (i.e., all patients have completed the study and all obligations have been fulfilled)

5. ASSESSMENT OF SAFETY

5.1 SAFETY PLAN

BFKB8488A is not approved, and clinical development is ongoing.

The safety plan for patients in this study is based on clinical experience with BFKB8488A in completed and ongoing studies. The anticipated important safety risks for BFKB8488A are outlined below. Please refer to the BFKB8488A Investigator's Brochure for a complete summary of safety information.

Several measures will be taken to ensure the safety of patients participating in this study. Eligibility criteria have been designed to exclude patients at higher risk for toxicities. Patients will undergo safety monitoring during the study, including assessment of the nature, frequency, and severity of adverse events. In addition, guidelines for managing adverse events, including criteria for dosage modification, treatment interruption or discontinuation, are provided below.

5.1.1 Risks Associated with BFKB8488A

[REDACTED]

[REDACTED]. For a detailed description of all the risks, please refer to the Investigator's Brochure. The risks described below include those that require additional monitoring and specific intervention.

5.1.1.1 Gastrointestinal Effects

Mild to moderate GI adverse events, namely nausea, vomiting, and diarrhea have been observed in the highest dose cohorts of the Phase 1a Study GC29819. Nausea, vomiting, and diarrhea were self-limited in all cases up to the 342 mg SC dose; however, at 681 mg SC, 6 out of 8 patients in the cohort reported adverse events of mild to moderate nausea. Four of the patients required medical intervention including intravenous fluids, ondansetron, metoclopramide, and/or loperamide. [REDACTED]

[REDACTED] However, GI adverse events were lower in frequency and severity, and better tolerated at the other doses including those proposed in this study.

Patients should be closely monitored for GI adverse events and early intervention is recommended. Patients should be treated as necessary according to standard of care (see [Table 1](#)).

5.1.1.2 Injection Site Reaction/Allergic or Anaphylactic Reactions to BFKB8488A

Monoclonal antibodies such as BFKB8488A may be associated with localized reactions at the site of injection. Systemic injection-related reactions as well as allergic or anaphylactic reactions could possibly also occur. These reactions can be severe or even life threatening.

Patients will be monitored for these types of reactions during and after receiving BFKB8488A and treated as per institutional guidelines. Study personnel will monitor for any injection-site reactions (per criteria in [Appendix 4](#)) or drug-related toxicities such as anaphylactic and other hypersensitivity reactions after receiving BFKB8488A, *including assessing vital signs as clinically indicated.*

5.1.1.3 Loss of Lean Body Mass or Bone Mineral Density Related to Weight Loss

[REDACTED]
In the dose ranging Phase Ib multiple-dose study in humans, there was no significant difference overall between the BFKB8488A- and placebo-treated patients. [REDACTED]

[REDACTED]
Additional tests may be done if clinically indicated. Reported fractures will be closely monitored by

the Sponsor for non-traumatic causes. Patients will be provided guidance regarding the recommended daily allowance for vitamin D and calcium per the Institute of Medicine 2011 recommendation.

5.1.1.4 Effect on Hypothalamic-Pituitary Axis

Because there are reports of increased corticosterone production in FGF21 transgenic mice, an important safety consideration is the potential for impact on the hypothalamic-pituitary- adrenal (HPA) axis. BFKB8488A given once intraperitoneally at 25 mg/kg induced a very modest increase in plasma corticosterone in lean chow-fed C57BL/6 mice; however, a similar drug-related response was not observed in diet-induced obese mice.

The exclusion criteria are designed to exclude patients with abnormalities in thyroid function test at screening (including subclinical disease, as well as patients being treated for *hyperthyroidism and patients being treated for hypothyroidism who are not on stable treatment*), any form of Cushing's syndrome (including pituitary Cushing's disease, known adrenal insufficiency by clinical history, or patients taking systemic glucocorticoid at baseline), growth hormone deficiency, or acromegaly.

Hypothalamic-pituitary axis function will be monitored by evaluating changes in free T4, TSH, IGF-1, ACTH, and 24-hour urinary cortisol and creatinine in this study. Additional specific tests of pituitary function may be performed at the discretion of the investigator or Sponsor on the basis of emerging safety data during the course of this study.

5.1.1.5 Sympathetic Effects

There were no meaningful changes from baseline in mean body temperature, and no adverse events of fever were reported.

The patients' vital signs including heart rate, blood pressure, and temperature will be monitored closely throughout the study, including triplicate measurements of blood

pressure. Marked hypertension as defined by a systolic blood pressure ≥ 180 mmHg that is at least 20 mmHg higher than the baseline measurement will be considered an adverse event of special interest, immediately reportable to the Sponsor (see Section 5.2.3).

5.1.1.6 Hypoglycemia

In murine models, BFKB8488A induced antibody-mediated activation of FGFR1/KLB complex and improvements in obesity-associated metabolic derangements including hyperglycemia (Kolumam et al. 2015). [REDACTED]

Patients will be monitored for signs and symptoms of hypoglycemia and have blood glucose measured at baseline and throughout study. Patients with T2DM will also be provided with a home glucose monitor, supplies, and training to monitor their fasting blood glucose levels at least twice weekly or if they experience any symptoms of hypoglycemia. Patients taking insulin will have more frequent home glucose monitoring as instructed in Section 4.5.11.

5.1.1.7 CNS Effects

[REDACTED] Additionally, to assess the potential CNS effects, mood, suicidal ideation and behavior will be assessed in the study for the duration of this trial by administration of the C-SSRS every 2 weeks. Prospective scales that monitor depression such as the PHQ-9 will also be administered periodically.

5.1.1.8 Exocrine Function of Pancreas

[REDACTED] Patients that develop diarrhea should be monitored for steatorrhea and, if needed, for malabsorption.

5.1.2 Management of Patients Who Experience Adverse Events

5.1.2.1 Dose Modifications

In the fixed dose arms, there will be no dose modifications (dose reductions) for BFKB8488A or placebo in this study due to adverse events in individual patients. [REDACTED]

5.1.2.2 Treatment Interruption

BFKB8488A treatment may be temporarily suspended in patients who experience a treatment-emergent adverse event considered to be related to study drug. If the event improves to Grade 1 or better, treatment will resume at the next scheduled dose. If one or more scheduled dose is missed because of an ongoing adverse event, the study treatment may be restarted based on the investigator's judgment. Study treatment may be suspended for reasons other than a treatment-emergent adverse event (e.g., surgical procedures) with Medical Monitor approval. The investigator and the Medical Monitor will determine the acceptable length of treatment interruption.

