4.5 STUDY ASSESSMENTS

The schedule of activities to be performed during the study is provided in [REDACTED]. All activities should be performed and documented for each patient.

Patients will be closely monitored for safety and tolerability throughout the study. Patients should be assessed for toxicity prior to each dose; dosing will occur only if the clinical assessment and local laboratory test values are acceptable.

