4.6 TREATMENT, PATIENT, STUDY, AND SITE DISCONTINUATION

4.6.1 Study Treatment Discontinuation

Patients must permanently discontinue study treatment if they experience any of the following:

- Any medical condition that the investigator or Sponsor determines may jeopardize the patient's safety if he or she continues to receive study treatment
- Investigator or Sponsor determination that treatment discontinuation is in the best interest of the patient
- Pregnancy
- Any adverse event CTCAE Grade 4 or higher, regardless of attribution to study drug
- Positively detected suicidal ideation type 4 or 5 or suicidal behavior
- 24-hour urinary cortisol $>1.5 \times$ ULN and $>2 \times$ baseline, if confirmed on follow up visit within 2 weeks.
- If any signs or symptoms of hyper- or hypothyroidism that accompany changes in thyroid function tests (TSH or free T4) that are confirmed by repeat testing.
- Abnormal IGF-1 that is confirmed by repeat testing.
- Nontraumatic bone fracture

The primary reason for study treatment discontinuation should be documented on the appropriate eCRF. Patients who discontinue study treatment prematurely will not be replaced. Patients who discontinue treatment prior to study treatment completion will participate in the end-of-treatment visit at the time of early discontinuation and will enter a follow-up period for a total of 6 weeks.

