5.1.2.3 Management Guidelines

Toxicities associated or possibly associated with study treatment should be managed according to the management guidelines provided in this protocol or, if not specifically mentioned, according to standard medical practice.

In general, events of Grade 1 and 2 severity as per the Common Terminology Criteria for Adverse Events (CTCAE) scale should be treated symptomatically if needed while continuing the use of BFKB8488A. Study drug must be interrupted in instances of CTCAE Grade 3 adverse events related to study drug, and discontinued if they do not resolve to Grade 1 with symptomatic treatment or standard of care, or recur following resumption of dosing. All cases of CTCAE Grade 4 regardless of attribution require study drug discontinuation. A detailed list of adverse events and laboratory abnormalities necessitating study treatment discontinuation is included in Section [4.6.1](#).

Guidelines for management of specific adverse events are outlined in [Table 1](#).

Table 1 Guidelines for Management of Patients Who Experience Specific Adverse Events

| Event | Action to Be Taken |
|----------------------------|--|
| Nausea and vomiting | |
| Grade 1 or 2 | 
 • Treat with antiemetics as per local standard of care. • Provide fluid and electrolyte replacement if necessary. • If nausea occurs for less than 7 consecutive days, continue study drug. • If nausea occurs for more than 7 consecutive days, hold study drug until nausea reaches Grade 1 or resolves and then resume study drug. • [REDACTED] |
| Grade 3 | 
 • Withhold study drug. • Provide supportive treatment as per local standard of care. • After improvement to Grade 1 or resolution of symptoms and consultation with the Medical Monitor, resume study drug • [REDACTED] |
| Grade 4 | 
 • Discontinue study drug. • Treat per local standard of care. |
| Diarrhea | |
| Grade 1 or 2 | 
 • Continue study drug. • Treat with antidiarrheal agents as per local standard of care. • Provide fluid and electrolyte replacement if necessary • Evaluate for steatorrhea and, if needed, for malabsorption and treat as per local standard of care. |

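### After a first related Grade 3 systemic allergic or anaphylactic reaction that clears before the next dose, the written default is to resume, and a stop rests on judgment

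*Combined protocol and SAP*

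**What the plan says.** Section 5.1.2.2 allows temporary suspension for an event considered related to study drug and then states: "If the event improves to Grade 1 or better, treatment will resume at the next scheduled dose". If a scheduled dose was missed because the event was still ongoing, restarting is left to the investigator. The section ends: "The investigator and the Medical Monitor will determine the acceptable length of treatment interruption".

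Under Section 5.1.2.3, a related Grade 3 event must lead to interruption, and the drug is to be "discontinued if they do not resolve to Grade 1 with symptomatic treatment or standard of care, or recur following resumption of dosing". Grade 4 events stop the drug whatever their cause. Toxicities are otherwise managed by the protocol's own guidelines "or, if not specifically mentioned, according to standard medical practice".

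Section 4.6.1 lists the conditions for permanent discontinuation. It opens with a judgment clause, "Any medical condition that the investigator or Sponsor determines may jeopardize" the patient's safety if treatment continues, and a second clause on the patient's best interest. The specific entries include "Nontraumatic bone fracture".

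On the reactions themselves, Section 5.1.1.2 recognizes that they may be severe or life threatening, and provides for monitoring and for treatment under institutional guidelines. Section 5.1.2.4 sends anaphylaxis to Appendix 5. Section 4.1.2 excludes patients with a history of severe reactions of this kind.

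**The concern.** The general Grade 3 rule (interrupt, let the event clear, resume, stop if it comes back) suits toxicities where a second episode is an acceptable way to learn whether the drug is tolerated. A systemic allergic reaction is different, because the second exposure is itself the hazard. The protocol treats the risk as potentially life threatening and will not enroll a patient with a severe history. Yet a patient who acquires that history on study drug falls under the same resume sentence as any other related event.

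Two things are at stake. One is re-exposure of a patient who has just had a severe systemic reaction; in the fixed-dose arms "there will be no dose modifications (dose reductions) for BFKB8488A or placebo in this study due to adverse events in individual patients", so a resumed dose is the full assigned dose. The other is consistency: where a stop needs a case-by-case decision against a written default, sites can decide differently.

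**Working it through.** No arithmetic applies, and the plan states no figure on this point. The check traces one case through the rules: a systemic allergic or anaphylactic reaction, related to study drug, graded 3, and back to Grade 1 or better before the next two-weekly dose.

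1. **Interruption (5.1.2.3).** Required, because the event is Grade 3 and related.
2. **Stop for non-resolution (5.1.2.3).** Not met; the event has cleared.
3. **Resumption (5.1.2.2).** The resume sentence applies. The sentence on investigator judgment does not, because no dose was missed for an ongoing event. The closing sentence on length of interruption would allow a longer pause but does not require one.
4. **Stop for recurrence (5.1.2.3).** This is the only remaining Grade 3 stop, and it operates only after the patient has been dosed again.
5. **Grade 4 rule (5.1.2.3 and 4.6.1).** Not met.
6. **Event-specific stop.** None found:
   - Section 4.6.1 has 9 entries: 2 judgment clauses, the Grade 4 rule and 6 specific conditions. None of the 6 is an allergic or anaphylactic reaction.
   - Table 1 has 4 event groups: nausea and vomiting, diarrhea, hypertension, and liver enzymes.
   - Section 5.1.2.4 covers local reactions and the pointer to Appendix 5. It has no wording on continuing, holding or stopping.
   - Appendix 5 has 8 steps on acute care and sampling. Step 1 stops the injection in progress, not the course. Step 8 refers to a washout where appropriate, which allows for a stop without requiring it.

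The visible text of Sections 4.6.1, 5.1.2.2 and 5.1.2.4 and of Appendix 5 shows no redaction mark where such a rule would sit.

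The protocol is more explicit for other events:

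| Event | Written rule on further dosing |
|---|---|
| Nontraumatic fracture (4.6.1, 5.1.2.5) | Stop at first occurrence |
| Confirmed cortisol or IGF-1 abnormality (4.6.1, 5.1.2.7) | Stop |
| Sustained QTcF prolongation (5.1.2.9) | Stop, unless another cause is clear |
| Mood or suicidality signal (5.1.2.8) | Hold for psychiatric evaluation and/or stop |
| Glucose of 270 mg/dL or more (5.1.2.6) | Medical Monitor decides on continuation |
| Grade 3 nausea/vomiting, diarrhea or hypertension; liver-enzyme interruption (Table 1) | Medical Monitor contact before restart |
| Grade 3 systemic allergic or anaphylactic reaction (5.1.2.4, Appendix 5) | None specific; general resume rule |

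Of Sections 5.1.2.4 to 5.1.2.9, Section 5.1.2.4 is the only one silent on further dosing.

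**The case against.** The strongest reply is that the protocol relies on physicians and gives them what they need. Section 4.6.1 is mandatory once the investigator or Sponsor determines that continuing may endanger the patient, and the resume sentence governs suspended patients, not discontinued ones. Section 4.5 adds that "dosing will occur only if the clinical assessment and local laboratory test values are acceptable". Doses are given by a healthcare professional with a physician available (4.3.2.1), patients are monitored for these reactions and treated under institutional guidelines (5.1.1.2), and standard medical practice fills gaps (5.1.2.3). Serious events reach the Sponsor within 24 hours (5.2.2), and the monitoring committee reviews unblinded safety data (3.1.2). Table 1 also shows that the resume sentence is not applied literally everywhere: restart there is often optional and follows a discussion.

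Most of this stands. A reader might infer that the protocol compels re-dosing after anaphylaxis; it does not, because any of these routes can prevent it and the Section 4.6.1 clauses override the resume sentence once used.

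What does not follow is that the gap is harmless. Each route needs someone to decide against the default. A patient whose reaction has fully cleared could pass a pre-dose assessment. The standard-practice fallback is for matters not specifically mentioned, whereas related Grade 3 events are expressly covered, so a site could reasonably follow the written rule. The softer restart wording in Table 1 belongs to events listed there, and these reactions are not. Section 5.2.3 does not list them among its 7 events of special interest, and one Grade 3 event does not meet the ad hoc review triggers named in Section 3.1.2, although that list is not exhaustive.

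**Conclusion.** The point holds for one case: a first related Grade 3 systemic reaction that clears before the next dose. For it the written default is resumption, the only remaining mandatory Grade 3 stop comes after re-exposure, and a stop at the first event depends on judgment. This is more than missing detail, because a stated rule points the wrong way for a risk the protocol itself treats as an entry bar. It should be corrected, though the judgment safeguards keep it from being a defect that forces harm.

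No numerical size should be attached. Section 1.3 reports no hypersensitivity reactions in the single-dose Phase Ia study, so the event is probably rare. The documents give no rate under repeated dosing and do not reproduce the CTCAE grading of anaphylaxis. The conclusion assumes only that some such reactions would be graded 3.

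A reader might also infer that a patient who reacts early could go on to receive most of the 26 doses despite repeated reactions. The documents do not support that: a Grade 3 event that recurs after restart must lead to discontinuation. The exposure at issue is the re-dosing that follows the first reaction.

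**What to change.** 1. **Section 4.6.1:** add an entry such as *Anaphylaxis, or a systemic hypersensitivity reaction of Grade 3 or higher, related to study drug, judged on the clinical picture even where signs are recorded separately under Section 5.3.5.1*. The last clause is needed because Section 5.3.5.1 has sites record reactions within 24 hours of dosing as individual signs, not as a diagnosis.
2. **Section 5.1.2.2:** except these reactions from the resume sentence.
3. **Section 5.1.2.3:** except them from the resolve-or-recur rule for Grade 3 events, so that the drug stops at the first event.

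Some judgment remains, on relatedness and on whether separate signs amount to a systemic reaction, but the decision to re-dose no longer depends on it.

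The cost is one entry and two exceptions, and possibly a few more permanent treatment stops. Those patients stay in the mITT population, which Section 6 defines by receipt of at least one dose, though Section 4.6.1 brings their end-of-treatment visit forward. The 10% in the synopsis sample-size text is loss to follow-up and should not be cited as an allowance for these stops.

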5.1.2.3 Management Guidelines

Toxicities associated or possibly associated with study treatment should be managed according to the management guidelines provided in this protocol or, if not specifically mentioned, according to standard medical practice.

In general, events of Grade 1 and 2 severity as per the Common Terminology Criteria for Adverse Events (CTCAE) scale should be treated symptomatically if needed while continuing the use of BFKB8488A. Study drug must be interrupted in instances of CTCAE Grade 3 adverse events related to study drug, and discontinued if they do not resolve to Grade 1 with symptomatic treatment or standard of care, or recur following resumption of dosing. All cases of CTCAE Grade 4 regardless of attribution require study drug discontinuation. A detailed list of adverse events and laboratory abnormalities necessitating study treatment discontinuation is included in Section [4.6.1](#).

Guidelines for management of specific adverse events are outlined in [Table 1](#).

Table 1 Guidelines for Management of Patients Who Experience Specific Adverse Events

| Event | Action to Be Taken |
|----------------------------|--|
| Nausea and vomiting | |
| Grade 1 or 2 | 
 • Treat with antiemetics as per local standard of care. • Provide fluid and electrolyte replacement if necessary. • If nausea occurs for less than 7 consecutive days, continue study drug. • If nausea occurs for more than 7 consecutive days, hold study drug until nausea reaches Grade 1 or resolves and then resume study drug. • [REDACTED] |
| Grade 3 | 
 • Withhold study drug. • Provide supportive treatment as per local standard of care. • After improvement to Grade 1 or resolution of symptoms and consultation with the Medical Monitor, resume study drug • [REDACTED] |
| Grade 4 | 
 • Discontinue study drug. • Treat per local standard of care. |
| Diarrhea | |
| Grade 1 or 2 | 
 • Continue study drug. • Treat with antidiarrheal agents as per local standard of care. • Provide fluid and electrolyte replacement if necessary • Evaluate for steatorrhea and, if needed, for malabsorption and treat as per local standard of care. |
| Grade 3 | 
 • Withhold study drug. • Provide supportive treatment as per local standard of care. • Evaluate for steatorrhea and malabsorption and treat as per local standard of care. • If the event improves to Grade 1 or less prior to the next scheduled dose, study drug may be resumed after discussion with the Medical Monitor. |
| Grade 4 | 
 • Discontinue study drug. • Treat per local standard of care. |

Table 1 Guidelines for Management of Patients Who Experience Specific Adverse Events (cont.)

| Event | Action to Be Taken |
|---|--|
| Hypertension | |
| Grade 1 | 
 Continue study drug. If >20 mm Hg increases on 2 visits, consider starting anti-hypertensive medication. |
| Grade 2 | 
 Continue study drug. Increase or start anti-hypertensive medication as per local standard of care. Closely monitor blood pressure. |
| Grade 3 | 
 Withhold study drug. Manage marked acute hypertension as per institutional guidelines. If the event improves to Grade 1 or less prior to the next scheduled dose, study drug may be resumed after discussion with the Medical Monitor. |
| Grade 4 | 
 Discontinue study drug. Treat per local standard of care. |
| Increased Liver Enzymes | |
| In patients with BLM of ALT and AST $<1.5 \times$ ULN: If ALT or AST $>3 \times$ ULN or TBL $>1.5 \times$ BLM OR In patients with BLM of ALT or AST $>1.5 \times$ ULN: If AST or ALT $>2 \times$ BLM or TBL $>1.5 \times$ BLM | 
 Repeat testing of ALT, AST, ALP and TBL within 48–72 hours, with inquiry about symptoms. 
If repeat testing above confirms initial result:
 
 Repeat ALT, AST, ALP, and TBL two or three times weekly. Frequency of retesting can decrease to once a week or less if abnormalities stabilize or the trial drug has been discontinued and the subject is asymptomatic. Obtain a more detailed history of symptoms and prior or concurrent diseases. Obtain a history of concomitant drug use (including nonprescription medications and herbal and dietary supplement preparations), alcohol use, recreational drug use, and special diets. Rule out acute viral hepatitis types A, B, C, D, and E; autoimmune or alcoholic hepatitis; NASH; hypoxic/ischemic hepatopathy; and biliary tract disease. Obtain a history of exposure to environmental chemical agents. Obtain additional tests to evaluate liver function, as appropriate (e.g., INR, direct bilirubin). Consider gastroenterology or hepatology consultations. Consider liver biopsy |

Table 1 Guidelines for Management of Patients Who Experience Specific Adverse Events (cont.)

| Event | Action to Be Taken |
|--|--|
| Increased Liver Enzymes (cont.) | |
| In patients with BLM of ALT and AST $<2 \times$ ULN: If ALT or AST increases to $>5 \times$ BLM | 
 Interrupt or discontinue BFKB8488A. |
| In patients with BLM of ALT and AST $\geq 2 \times$ ULN but $<5 \times$ ULN: If ALT or AST increases to $>3 \times$ BLM | 
 Interrupt or discontinue BFKB8488A. |
| In patients with BLM of ALT and AST $\geq 5 \times$ ULN: If ALT or AST increases to $>2 \times$ BLM | 
 Interrupt or discontinue BFKB8488A. |
| In patients with BLM in normal range or ALT or AST $<1.5 \times$ ULN: If ALT or AST increases to $>3 \times$ ULN accompanied by: 
 a concomitant increase in TBL to $>2 \times$ ULN 
OR
 
 the INR concomitantly increases by > 0.2 in any patients with signs and symptoms of fatigue, nausea, vomiting, right upper quadrant pain or tenderness, fever, rash, and/or eosinophilia ($> 5\%$) | 
 Interrupt or discontinue BFKB8488A. |
| In patients with BLM of ALT or AST $> 1.5 \times$ ULN: If ALT or AST increases to $>2 \times$ BLM accompanied by: 
 a concomitant increase in TBL to $>2 \times$ BLM 
OR
 
 the INR concomitantly increases by > 0.2 in any patients with signs and symptoms of fatigue, nausea, vomiting, right upper quadrant pain or tenderness, fever, rash, and/or eosinophilia ($> 5\%$) | 
 Interrupt or discontinue BFKB8488A. |
| | 
 In all the above instances, continue monitoring the liver enzymes. If the levels of liver enzymes return to baseline levels, or alternate causes are clearly identified, resumption of dosing may be considered in some cases after discussion with the Medical Monitor. |

BLM=baseline measurement; INR=International Normalized Ratio; TBL=total bilirubin; ULN=upper limit of normal.

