4.3.2 Study Treatment Dosage, Administration, and Compliance

The treatment regimens are summarized in Section [3.1](#).

Refer to the pharmacy manual for detailed instructions on drug preparation, storage, and administration.

Any dose modification should be noted on the Study Drug Administration electronic Case Report Form (eCRF). Cases of accidental overdose or medication error, along with any associated adverse events, should be reported as described in Section [5.3.5.12](#).

Guidelines for dosage modification and treatment interruption or discontinuation for patients who experience adverse events are provided in Section [5.1.2](#).

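### For a drug-related Grade 3 event that recurs, 5.1.2.2 tells sites to resume where 5.1.2.3 tells them to stop; for an unresolved event 5.1.2.2 is ambiguous, and the 4.6.1 stop list carries neither Grade 3 stop

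*Combined protocol and SAP*

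**What the plan says.** Four places in the protocol govern what a site does after a drug-related Grade 3 event.

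- **5.1.2.3 Management Guidelines.** Interruption is mandatory, and study drug is to be "discontinued if they do not resolve to Grade 1 with symptomatic treatment or standard of care, or recur following resumption of dosing". The next sentence requires discontinuation for every Grade 4 event. The section then refers the reader onward: "A detailed list of adverse events and laboratory abnormalities necessitating study treatment discontinuation is included in Section" 4.6.1.
- **5.1.2.2 Treatment Interruption.** This covers any related treatment-emergent event, with no limit on grade. It says: "If the event improves to Grade 1 or better, treatment will resume at the next scheduled dose". If one or more doses "is missed because of an ongoing adverse event, the study treatment may be restarted based on the investigator's judgment". It closes with: "The investigator and the Medical Monitor will determine the acceptable length of treatment interruption".
- **4.6.1 Study Treatment Discontinuation.** The list opens with "Patients must permanently discontinue study treatment if they experience any of the following". Its only item that names a CTCAE grade is "Any adverse event CTCAE Grade 4 or higher, regardless of attribution to study drug".
- **Table 1 in 5.1.2.3.** The Grade 3 rows for nausea and vomiting, diarrhea and hypertension each require withholding the drug, improvement to Grade 1 and contact with the Medical Monitor before restart. The diarrhea and hypertension rows address only improvement that occurs before the next dose is due. Raised liver enzymes have their own restart condition: a return to baseline levels or a clear alternate cause.

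Section 4.3.2 sends sites to the whole of 5.1.2: "Guidelines for dosage modification and treatment interruption or discontinuation for patients who experience adverse events are provided in Section" 5.1.2. No order of precedence among its subsections is stated.

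**The concern.** A site that works from 5.1.2.2, or that checks only the 4.6.1 list, could re-dose a patient whom 5.1.2.3 requires to stop. In the fixed dose arms 5.1.2.1 rules out dose reduction for adverse events in individual patients, and 5.1.2.9 mentions a lower dose only for QT findings. Apart from that QT case, a mistaken restart in those arms would be at the full assigned dose. Sites could also treat like patients differently. The protocol itself regards related Grade 3 events as important: under 3.1.2, three patients with the same attributed Grade 3 event trigger an ad hoc unblinded review by the Internal Monitoring Committee.

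**Working it through.** No alpha, power or rate is involved, so the check sets the rules side by side for each course that a related event can take.

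| Course of a drug-related event | 5.1.2.3 | 5.1.2.2 | 4.6.1 | Result |
|---|---|---|---|---|
| Grade 3, first episode, improves to Grade 1 | No stop | Resume | No stop | Agree |
| Grade 3, recurs after restart, improves to Grade 1 again | Discontinue | Resume, no exception | Not listed | Conflict |
| Grade 3, stays above Grade 1, doses missed | Discontinue, no time limit given | May restart on judgment, no grade stated | Not listed | Ambiguous |
| Grade 4 | Discontinue | No exception stated | Discontinue | Stop stated in two places |

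**Recurrent event.** The resume sentence in 5.1.2.2 is directive and applies to any related event that reaches Grade 1. A second episode that settles meets its condition. Under 5.1.2.3 the same patient has met a stop condition. The two instructions cannot both be followed.

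**Unresolved event.** The missed-dose sentence names no grade. It follows a sentence that has already dealt with events reaching Grade 1, so it can be taken to cover those that have not. It can equally be taken in sequence: after missed doses, restart is no longer automatic and needs judgment. The wording does not settle which is meant.

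**Count for 4.6.1.** The items are: medical condition jeopardizing safety; investigator or Sponsor determination; pregnancy; Grade 4 or higher; suicidality; urinary cortisol; thyroid; IGF-1; nontraumatic fracture. That is 9 items, of which 1 names a CTCAE grade and 0 name Grade 3. In 5.1.2.3 the Grade 3 and Grade 4 stops stand in consecutive sentences, yet only the Grade 4 stop appears in the list.

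**Count for Table 1.** There are 3 symptom rows at Grade 3. All 3 require Grade 1 and Medical Monitor contact, and 0 allow restart above Grade 1. Two of the 3 (diarrhea and hypertension) are tied to improvement before the next dose. The intended threshold is therefore clear for listed events. A related Grade 3 event with no row depends mainly on 5.1.2.2, 5.1.2.3 and 4.6.1.

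**The case against.** The strongest reply is that 5.1.2.3 is the specific, mandatory rule and 5.1.2.2 the general, permissive one, so the specific rule controls. 4.3.2 sends sites to all of 5.1.2, which includes 5.1.2.3. Section 4.5 requires a toxicity assessment before each dose and allows dosing only if the findings are acceptable. The Medical Monitor has a say in how long an interruption may last. Section 1.3 repeats the stop for a Grade 3 event that does not resolve.

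Most of this stands for the unresolved event and is why that part is called ambiguous. A reader might infer that 5.1.2.2 authorizes dosing above Grade 1. It does not say so, and the sequential reading is natural. The reply is weaker for the recurrent event. There the sentence in 5.1.2.2 is itself directive, and Section 1.3 leaves out recurrence and words the Grade 3 rule as a recommendation.

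A reader might also infer that omission from 4.6.1 cancels the Grade 3 stops. It does not: 5.1.2.3 states them in full, and the list is not exhaustive, since the QT stops in 5.1.2.9 are absent too. The two judgment items in 4.6.1 could catch these patients, but only by discretion.

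Two further inferences are unsupported. The related Grade 3 gastritis in the Phase Ib study resolved, so it is not an example of wrongful re-dosing. And the Grade 3 nausea and vomiting row ends in a redacted bullet, so nothing can be said about how it handles recurrence.

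**Conclusion.** The inconsistency is real and modest. For a recurrent related Grade 3 event, 5.1.2.2 and 5.1.2.3 conflict. For an unresolved one, 5.1.2.2 is ambiguous. 4.6.1 omits both stops while carrying the Grade 4 stop. The practical risk is limited to sites that apply 5.1.2.2 or 4.6.1 without 5.1.2.3, mainly for Grade 3 events with no Table 1 row. The documents give no basis for estimating how many patients this would affect, and the number may be zero. The conclusion assumes that the visible text of 5.1.2.2 and 4.6.1 is complete; no redaction shows in either. The edit is worth making because it concerns patient safety and costs almost nothing.

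**What to change.** 1. In 5.1.2.2, make both the sentence on resuming at Grade 1 and the sentence on restart after missed doses *subject to Sections 4.6.1 and 5.1.2.3 and, for events listed in Table 1, to the Table 1 restart conditions*. The Table 1 reference keeps the next-dose wording for diarrhea and hypertension from being loosened.
2. Add one item to 4.6.1: *Drug-related CTCAE Grade 3 adverse event that has not come down to Grade 1 within the interruption length agreed by the investigator and Medical Monitor (Section 5.1.2.2), or that returns after dosing is restarted; for raised liver enzymes follow Table 1.* The interruption length supplies the time limit that 5.1.2.3 lacks. The liver exception is needed because Table 1 sets its restart condition by baseline levels or an alternate cause, not by Grade 1.

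The cost is two short edits. No new Medical Monitor consultation is needed, and the handling of Grade 1, Grade 2 and unrelated events does not change. The downside is that a few patients whom a site might have restarted on judgment will be stopped, which 5.1.2.3 already requires.
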